9.7.3 Analysis of primary outcome(s)

Adverse events will be summarized for the safety population using NCI-CTCAE v4.03 as well as the Medical Dictionary for Regulatory Activities (MedDRA). Incidence proportions will be calculated based on the total number of patients valid for safety. Incidence proportions will be calculated by MedDRA system organ class, preferred term and worst CTCAE grade, for the MedDRA-based analyses, and by Event Category/NCI CTC Term and worst grade for the CTCAE-based analyses. These analyses will be performed for TEAEs, drug-related TEAEs, treatment-emergent SAEs, drug-related treatment-emergent SAEs, and TEAEs leading to dose reduction, dose interruption, or permanent dose discontinuation.

Subgroup analyses stratified by prognostic/predictive factors including liver function-related factors, tumor extent/stage, general condition such as ECOG performance status and comorbidities collected at baseline, including hepatic etiology [hepatitis C virus (HCV), hepatitis B virus (HBV), and alcoholic and nonalcoholic steatohepatitis (NASH)], as mentioned above, may be explored. For ECOG performance status, frequencies of recorded values and changes from performance status at baseline will be tabulated by visit. For vital signs, descriptive statistics will be calculated by visit. Where possible, laboratory data will be graded using the mapping provided within the NCI CTCAE manual version that is valid at time of analysis. CTCAE severity grading for laboratory abnormalities is mainly based on applicable laboratory threshold values outlined in NCI-CTCAE manuals. Frequency of laboratory abnormalities will be tabulated by NCI-CTCAE category and worst grade.

Changes in laboratory data and in CTCAE grades for laboratory data will also be analyzed.

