For uHCC, sorafenib has been the only available systemic treatment. It demonstrated a statistically significant OS benefit, shown in two phase III randomized, placebo-controlled trials (SHARP and Asia Pacific study), [3] [4] and has been standard of care as the first-line option in patients with uHCC who are not suitable for curative treatments. [5] [6] [7] However, there has been no systemic therapy available after progression on sorafenib. A number agents have been evaluated for uHCC, none has shown a survival benefit, although recent reports from a phase III trial indicate that lenvatinib might be non-inferior to sorafenib as first-line treatment. [8] Recent data from the phase III RESORCE study showed clinically and statistically significant OS prolongation with regorafenib in patients with uHCC who have progressed on the first-line therapy of sorafenib. The median OS was 10.6 months for patients receiving regorafenib versus 7.8 months for those receiving placebo [HR 0.63 (95% CI: 0.50, 0.79); P<0.001], which translates to a 37% reduction in the risk of death over the study period. [9]

The phase III RESORCE data indicated that the safety profile of regorafenib in HCC was consistent with that reported in the phase III studies in mCRC and GIST. In all three indications, the most

common grade \geq 3 adverse events (AEs) included hand–foot skin reaction, hypertension, fatigue, and diarrhea, and AEs leading to discontinuation were relatively low (6–18% among all three studies). [9] [10] [11] [12]

The purpose of this observational study is to describe the safety and effectiveness of regorafenib in patients with uHCC under real-world practice conditions. Patients enrolled will be those for whom a decision to treat with regorafenib has already been made, and will likely include a variety of HCC patient subsets, such as patients grouped by Child–Pugh score regionally and globally, that were not addressed in the RESORCE study. The study will also provide information on treatment patterns and outcomes for patients with uHCC in the real-world setting, and will collect baseline information, including retrospective data on sorafenib treatment.

8. Research questions and objectives

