9.2.7 Visits

The start of the study is the date from which information on the first patient can be first recorded in the study dataset (i.e. first informed consent obtained). The end of the study is the date after which the final patient remaining in the study has been in the study for 24 months, or is no longer under observation owing to being lost to follow-up, withdrawal, or death.

A visit is defined as any status assessment or new treatment decision the treating physician takes in the presence of the patient. The time interval between two documented status assessments is assumed to be 6–12 weeks, although this will be at the discretion of the treating physician.

The investigator will document the baseline / initial visit, follow-up visits and the end of observation / final visit for each patient in the CRF. Follow-up visits occur during routine practice; the study protocol does not define exact referral dates for those visits. The end of observation / final visit is to be documented after a patient has been on study for at least 24 months, is lost to follow-up, has withdrawn consent or has died, whichever comes first. If the documentation is stopped prematurely, the reasons for the end of observation must be given. If a patient joins an interventional clinical study during the course of observation, information on survival should be collected up to the end of this study. If a patient remains alive at time of study closure, this will be documented in the final visit.

Table 3: Tabulated overview on variables collected during the study

Variables	Baseline / Initial visit*	Follow-up visit(s)	End of observation / final visit
Visit date	X	X	X
Eligibility assessment	X		
Patient information and consent	X		
Demography	X		
Co-morbidities (medical history, concomitant diseases)	X		
HCC classification	X		
Prior systemic anti-cancer therapy (including sorafenib) (see 9.3.3.6)	X		
Tolerability of prior systemic anti-cancer therapy (including sorafenib) (see 9.3.3.6)	X		
Prior local anti-cancer therapy	X		
Prior medication	X		
Lifestyle records (smoking & alcohol use)	X		
Vital signs	X		
BCLC Staging	X		
Tumor status and metastases (see 9.3.3.9)	X	X	X
Child-Pugh classification	X	X	X

ECOG performance status	X	X	X
Laboratory parameters (see 9.3.3.7)	X	X	X
Concomitant medication	X	X	X
Exposure/treatment with regorafenib (see 9.3.3.8)	X	X	X
Adverse events on regorafenib (see 9.3.3.11)	X	X	X**
Reason for end of observation			X
Death and reason for death			X

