9.3.3.3 Vital signs

Information on vital signs to be documented includes:

- Height
- Weight
- Blood pressure
- Heart rate

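### Vital signs are to be summarised by visit, but Table 3 collects them only at the Baseline / Initial visit, so no post-baseline summary can be produced

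*Protocol*

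**What the plan says.** Section 9.7.3 of the Protocol, which sets out the analysis of the primary (safety) outcome, states: "For vital signs, descriptive statistics will be calculated by visit". In the sentence before, it treats ECOG performance status in the same way: recorded values and "changes from performance status at baseline will be tabulated by visit".

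The collection schedule is in section 9.2.7, under the title "Table 3: Tabulated overview on variables collected during the study". It has three columns: Baseline / Initial visit, Follow-up visit(s), and End of observation / final visit. The vital-signs row is marked in the first column only. The ECOG row reads "ECOG performance status X X X", so it is marked in all three.

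Section 9.3.3.3, opening with "Information on vital signs to be documented includes", lists height, weight, blood pressure and heart rate and gives no timing. Section 7 says that the most common events of grade 3 or higher across the regorafenib phase III studies "included hand–foot skin reaction, hypertension, fatigue, and diarrhea".

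**The concern.** An analysis by visit needs values from more than one visit. Here the analysis section assumes repeated vital signs and the collection schedule provides a single record per patient. The footnote to Table 3 places the initial visit at the start of regorafenib, so that one record is not an on-treatment follow-up value.

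Safety is the primary objective, and blood pressure is the measured counterpart of a toxicity that the protocol itself singles out. Laboratory abnormalities have a measured backstop: laboratory values are scheduled in all three columns and, where possible, graded by CTCAE separately from what the investigator reports as an adverse event. Blood pressure has no such backstop. Under section 11.1, a finding becomes an adverse event largely when the investigator judges it clinically relevant or when it leads to a dose modification. Across about 30 countries that threshold may vary, and measured values would help to show whether it does.

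This is a prospective study. Routine readings that are not entered in the CRF at the time may be hard to recover later.

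**Working it through.** The protocol gives no numerical figure on this point, so the check sets its sections side by side.

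1. **What the analysis needs.** Section 9.7.3 plans vital-sign statistics by visit, and therefore values at follow-up and final visits as well as at baseline.

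2. **What the schedule supplies.** The relevant rows of Table 3:

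| Row in Table 3 | Baseline / Initial | Follow-up | Final | Columns marked |
|---|---|---|---|---|
| Vital signs | X | – | – | 1 of 3 |
| ECOG performance status | X | X | X | 3 of 3 |
| Child–Pugh classification | X | X | X | 3 of 3 |
| Laboratory parameters | X | X | X | 3 of 3 |

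Scheduled post-baseline vital-sign columns: 1 marked − 1 at baseline = 0. For ECOG, the other variable that section 9.7.3 tabulates by visit: 3 − 1 = 2.

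3. **Is the row misread?** The text was taken from a PDF, so a lost mark has to be considered. Rows near it keep all three marks, and the row for the reason for end of observation keeps a single mark in the last column. Column positions have survived, and the baseline-only marking is credible as written.

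4. **Does another section fill the gap?** Section 9.3.3.1 lists only the visit date as collected at every visit. Section 9.3.3.3 says what is recorded, not when. Section 9.3.3.9, on assessment of therapy, names tumor assessment, Child–Pugh and ECOG, not vital signs. No section schedules vital signs after the Baseline / Initial visit.

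5. **Can the SAP fill it?** Section 9.7.1 leaves derived variables, missing-data handling and table format to the SAP. None of these creates values that were not collected.

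6. **What remains analysable?** Section 9.1.1 defines the primary endpoint as the frequency of documented TEAEs, and section 9.3.1 lists AEs, SAEs and TEAEs leading to dose modification as its variables. Vital signs are not among them. Hypertension reported as an adverse event is still collected and CTCAE-graded under section 9.3.3.11.

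**The case against.** The strongest reply is that this is one sentence against one table row in a descriptive study, and that the primary endpoint does not use vital signs. That is correct and it limits the consequence. It does not make the planned table producible.

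Four stronger readings are tempting, and the protocol does not support them.

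- **That hypertension would rest wholly on adverse event reports.** Concomitant medication is recorded at all visits, with start date and indication (section 9.3.3.6), so new antihypertensive treatment would be visible. Pre-existing hypertension is captured at baseline (section 9.3.3.5). Source data verification covers adverse events in a sample of at least 125 patients (section 9.8.2). This evidence is indirect or partial, but it exists. Only the measured values are missing.
- **That the change from baseline planned in section 9.7.1 is a second contradiction.** That plan applies only where applicable, and for a variable scheduled once it is not applicable.
- **That tabulation by visit is itself unsound because visits are irregular.** Section 9.2.7 does say that "the study protocol does not define exact referral dates for those visits". But nothing equates a visit with a sequential visit number, and mapping irregular visits to time windows is ordinary SAP content.
- **That laboratory data share the defect.** They are scheduled in all three columns, and section 9.7.3 does not plan them by visit. It tabulates abnormalities by worst grade and analyses changes.

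It is also fair to say that the CRF is not shown and might capture vital signs at follow-up. If it does, Table 3 is the part that is wrong, and the two places still need reconciling.

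**Conclusion.** The point holds as an internal contradiction. Section 9.7.3 promises vital-sign statistics by visit, and Table 3 schedules no vital signs after the Baseline / Initial visit, so no post-baseline summary can be produced from the scheduled data.

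The loss is confined to measured on-treatment blood pressure, heart rate and weight as a check on adverse event reporting. The primary TEAE frequencies stand, and so does hypertension as a reported event. A reader might infer that the primary safety endpoint is compromised; sections 9.1.1 and 9.3.1 do not support that.

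The conclusion assumes that Table 3 is the operative collection schedule and that the CRF, not available here, follows it. It is worth correcting because it sits in the primary-outcome section, is certain on the text, and is cheap to put right.

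**What to change.** Reconcile section 9.7.3 with Table 3, in one of two ways.

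- **Preferred.** In Table 3, mark vital signs at the follow-up and end-of-observation columns, limited to blood pressure, heart rate and weight and qualified as recorded if measured in routine care. Make the same change in the CRF, which Annex 1 lists as draft v.06. The sentence in section 9.7.3 can then stay. Because only routinely measured values are entered, this fits the statement in section 10.1 that participation requires no additional diagnostic or monitoring process. The cost is a little more data entry per visit: four fields, if blood pressure is entered as systolic and diastolic. Values will be missing where they were not measured.
- **Otherwise.** Restrict the vital-sign analysis in section 9.7.3 to a baseline summary. This costs no data collection, but gives up measured on-treatment blood pressure in a study whose primary objective is safety.

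No change to the primary endpoint, the laboratory analysis or the visit schedule is needed.

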9.1 Study design

This is an international, prospective, open-label, multi-center, observational study. Patients with uHCC for whom a decision to treat with regorafenib has been made before enrollment will be

eligible for the study. The decision on the dose and duration of treatment is solely at the discretion of the treating physician, based on the recommendations written in the local product information. Examinations and the laboratory monitoring schedule will follow local label recommendations in line with local standard of care. No control arm is planned in this study because regorafenib is the only agent with proven survival benefit in patients with uHCC after prior sorafenib treatment; there is currently no alternative treatment available.

This study is designed to evaluate AEs in patients treated with regorafenib. It will also collect data to describe the effectiveness of regorafenib in uHCC, patterns of treatment, and the influence of baseline characteristics and treatment history.

Data will be collected from approximately 1000 patients globally over a total study period of 5 years, including 36 months' enrollment and 24 months' observation time from study entry. Interim data analyses for safety monitoring will be conducted with a minimum of 500 patients who have been observed for at least 4 months. The final analysis will be conducted after the final patient remaining in the study has been observed for 24 months or is no longer under observation due to withdrawal or death.

Patients will be observed from the time from the start of therapy with regorafenib until the end of observation owing to premature discontinuation, withdrawal of consent, or death, or until the end of the study.

Physicians participating in this study are recommended to include consecutive patients. The data for this study will be collected using an electronic case report form (CRF).

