9.3 Variables

The investigator collects historic data (demographic and clinical characteristics) from medical records if available, or else by interviewing the patient. Likewise, the investigator collects treatment related data during initial visit and follow-up visits. The investigator documents the study-relevant data for each patient in the CRF. The CRF is available upon request (see Table 4, Annex 1).

Information will be collected from laboratory tests performed according to the local standard of care. For potential TEAE reporting of any laboratory abnormalities please refer to section 11.

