9.3.3.7 Laboratory parameters

Laboratory parameters to be documented include (if available):

- Date of test
- Platelets
- Hemoglobin
- Erythrocytes
- Hematocrit
- Leukocytes
- International normalized ratio (INR)
- Alanine transaminase (ALT)
- Aspartate transaminase (AST)
- Alkaline phosphatase (ALP)
- Sodium
- Lactate dehydrogenase (LDH)
- Alpha fetoprotein (AFP) and AFP-L3
- C-reactive protein (CRP)
- Gamma-glutamyl-transferase (GGT)
- Creatinine
- Creatinine clearance (CrCl)
- Cholinesterase (ChE)
- Total bilirubin
- Albumin
- Des-Gamma-Carboxy Prothrombin (DCP)/ protein induced by vitamin K absence/antagonist-II (PIVKA-II)

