9.5 Study size

Data collected from 1000 patients with uHCC treated with regorafenib globally should allow for sufficient evaluation of safety monitoring of all treated patients, as well as different subsets of patients, including evaluations between subgroups based on region etc. With this number of patients, it is possible to observe at least one patient with a particular adverse event, if the true incidence rate for the AE is 0.2% (2:1000), with approximately 86% probability. A particular event with a true incidence rate of 0.5% could be observed in at least two patients with 96% probability, and in at least three patients with 87% probability. The following tables show the probabilities of observing one, two, or three patients with the event for different true incidence rates, with a sample size of 1000 patients.

True incidence rate of a particular event (%)	Probability of observing the event in			
	At least one patient	At least two patients	At least three patients	
0.1	0.6323	0.2642	0.0802	
0.2	0.8649	0.5943	0.3233	
0.3	0.9504	0.8013	0.5771	
0.4	0.9818	0.9089	0.7625	
0.5	0.9933	0.9599	0.8760	

The sample size is also supported by the feasibility based on a previous global study in 3000 patients with uHCC who received sorafenib. Based on the information from external experts and market research, we consider 30-35% of patients who are treated with sorafenib would be subsequently treated with regorafenib; therefore, 1000 patients would be feasible for this observational study.

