10.1 Ethical conduct of the study

This study is an observational study where regorafenib is prescribed in the customary manner in accordance with the terms of the marketing authorization. There is no assignment of a patient to a particular therapeutic strategy. The treatment decision falls within current practice and the prescription of the medicines is clearly separated from the decision to include the patient in the study. No additional diagnostic or monitoring process is required for participation or during the study. Epidemiological methods will be used for the analysis of the collected data.

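### Worst-grade laboratory tables can show more toxicity in subgroups that are simply tested more often, because test frequency is left to local practice

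*Protocol*

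**What the plan says.** The laboratory summary is fixed in section 9.7.3: "Frequency of laboratory abnormalities will be tabulated by NCI-CTCAE category and worst grade". The next sentence there adds that changes in laboratory values and in their CTCAE grades will also be analysed.

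The study does not control how often patients are tested:
- Section 9.1: "Examinations and the laboratory monitoring schedule will follow local label recommendations in line with local standard of care".
- Section 9.3: "Information will be collected from laboratory tests performed according to the local standard of care".
- Section 9.3.3.7 asks for laboratory values only where they exist: "Laboratory parameters to be documented include (if available".
- Section 10.1: "No additional diagnostic or monitoring process is required for participation or during the study".
- Section 9.2.7, on visits and not on laboratory tests: "The time interval between two documented status assessments is assumed to be 6–12 weeks, although this will be at the discretion of the treating physician".

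Safety is meant to be looked at by group. Section 9.5 justifies the 1000 patients by safety evaluation overall "as well as different subsets of patients, including evaluations between subgroups based on region etc". Section 9.1.4 counts safety analysis by Child–Pugh status and prior treatment among the strengths of the design. Section 9.7.1 provides for country analyses and for stratification by baseline characteristics and prior treatment, and section 9.7.3 allows subgroups by liver function.

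Section 9.9 warns about variable intervals between visits for PFS and TTP. For other outcomes it has one general remark that local guidelines may produce differences in treatment or reporting.

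**The concern.** A maximum over repeated tests cannot fall as tests are added, and it usually rises. Worst grade therefore compares fairly between groups only if the groups are tested about equally often. A fixed schedule would secure that, and this study deliberately has none. The planned groupings, region and country above all, are ones along which local monitoring habits may differ.

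The problem is separate from length of exposure: it remains if two groups are treated for exactly the same time. At stake is the reading of the liver tests (ALT, AST, bilirubin, INR) in patients with different liver function and from different regions. A difference in surveillance could be read as a difference in harm, and laboratory toxicity could be understated where testing is sparse.

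**Working it through.** **The plan's own figures.** The protocol gives no figure on this point. Its only sizing figures, the 15 probabilities in section 9.5, all reproduce to four decimals from the binomial distribution with n = 1000. For example, 1 − 0.998^1000 = 0.8649 for at least one event at 0.2%. The present point does not touch them.

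**Inputs.** From the documents: the worst-grade measure (9.7.3) and locally set testing (9.1, 9.3, 9.3.3.7, 10.1). Assumed: 24 weeks on treatment; tests every 6 weeks in one group and every 12 in the other; identical true risk in both. The 6 and 12 weeks are borrowed from the spacing of status assessments in 9.2.7, only to illustrate a two-fold difference. They give 24/6 = 4 and 24/12 = 2 tests per patient. The per-test probabilities, correlations and episode lengths are also assumptions.

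**1. Independent tests.** P(worst grade reaches the threshold) = 1 − (1 − p)^k for k tests.

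| p per test | 4 tests | 2 tests | Ratio |
|---|---|---|---|
| 0.02 | 1 − 0.98^4 = 7.8% | 1 − 0.98^2 = 4.0% | 2.0 |
| 0.05 | 1 − 0.95^4 = 18.5% | 1 − 0.95^2 = 9.8% | 1.9 |
| 0.10 | 1 − 0.90^4 = 34.4% | 1 − 0.90^2 = 19.0% | 1.8 |

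**2. Correlated tests, p = 0.05.** Each test result is a normal score √ρ·u + √(1 − ρ)·e, with u shared within the patient and the threshold at the 95th percentile. There were 200,000 simulated patients per setting.

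| ρ | 4 tests | 2 tests | Ratio | Share not seen with 2 tests |
|---|---|---|---|---|
| 0.5 | 14.5% | 8.8% | 1.6 | 1 − 8.8/14.5 = 39% |
| 0.8 | 10.7% | 7.5% | 1.4 | 1 − 7.5/10.7 = 30% |
| 0.9 | 8.8% | 6.8% | 1.3 | 1 − 6.8/8.8 = 23% |

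**3. One episode per affected patient.** P(detected) = min(1, duration/interval), with a true incidence of 30% in both groups.
- 4 weeks long: 30% × 4/6 = 20% against 30% × 4/12 = 10%; ratio 2.
- 8 weeks long: 30% against 30% × 8/12 = 20%; ratio 1.5.
- 12 weeks long: 30% against 30%; ratio 1.

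For the same true risk and a two-fold difference in spacing, the apparent ratio therefore runs from 1 to about 2. How long abnormalities last and how strongly repeated tests agree decide where it falls.

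**The case against.** The case against has real substance.

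- *The remedy is analysis-plan content.* Section 9.7.1 leaves derived variables, missing data and table formats to the SAP. This stands for the laboratory denominator: 9.7.3 states its denominator for adverse-event proportions, not for laboratory tables, so an unstated laboratory denominator is no fault here. It does not dispose of the point itself, because the protocol fixes the worst-grade measure.
- *Other laboratory summaries are planned.* Changes in values and grades are to be analysed (9.7.3), with change from baseline by time point where applicable (9.7.1). This helps, but it leaves the graded frequency table as it is.
- *The comparisons are descriptive and partly optional.* True: no hypothesis is tested, the liver-function subgroups are only a possibility, and no sentence commits to a worst-grade laboratory table by region. Yet 9.5 and 9.1.4 present subgroup safety as a purpose of the study, and a descriptive table can mislead as well.
- *The primary endpoint is documented TEAEs.* Clinically relevant laboratory findings, and those leading to dose modification, are also captured as adverse events (11.1, 11.2). This limits the consequences.
- *By-window tables have their own bias.* A value chosen without regard to grade can miss a transient peak. Limiting the denominator to tested patients raises frequencies where only sicker patients are tested. This stands, and it is why such a table should not replace worst grade.

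A reader might also infer that certain regions or Child–Pugh classes will look worse, or that about half of the events (1 − 9.8/18.5 = 47%) go unseen under sparse testing. The documents support neither. They give no testing rates by group, and they do not say that poorer liver function brings more tests. The 6–12 weeks describes status assessments, not laboratory tests. The 47% requires independent tests within a patient, which is implausible for liver parameters.

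**Conclusion.** The point holds in conditional form. The protocol fixes a measure that depends on the number of tests, leaves that number to local practice, and intends to look at safety by groups in which local practice may differ. Section 9.9 recognises the mechanism for PFS and TTP and does not carry it over to laboratory data.

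The direction follows from arithmetic: at equal true risk, more tests cannot lower the observed worst grade. The actual size is unknown. If groups do not differ in testing rate there is no distortion, and a true difference in the opposite direction could mask it. The study's sizing and its analysis of reported TEAEs are unaffected. This is an inexpensive improvement to what the subgroup tables can support, not an error in the overall worst-grade table.

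**What to change.** Keep the worst-grade tables and add to section 9.7.3:

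1. Any worst-grade laboratory table by subgroup also shows, for each group, the number of patients tested post-baseline and the median number of tests per patient-month on treatment.
2. It is accompanied by a supplementary table of grades per fixed time window since first dose, with one value per patient per window, chosen without regard to grade, among patients tested in that window.
3. Subgroup differences in worst grade are not to be read as differences in toxicity where testing rates differ.

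In section 9.9, extend the warning on variable intervals from PFS and TTP to laboratory data.

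The test date (9.3.3.7) and the treatment start and stop dates (9.3.3.8) are already collected, so no visit, test or CRF field is added. The cost is some extra programming. The windowed table can miss transient peaks and does not remove selective testing of sicker patients. It therefore supplements worst grade, and the testing rates make uneven testing visible.
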